7.6 Pregnancy

If a female subject becomes pregnant during the treatment period or within 6 months after the last study medication application, a Pregnancy Report form should be completed and submitted to NFlection within 24 hours of learning of the pregnancy:

NFlection Medical Monitor

Email: [contact]

24-hour [contact]

Abortion, whether therapeutic or spontaneous, will also be reported on a Pregnancy Report form and sent to NFlection. If the abortion meets seriousness criteria, this information will be captured on the AE CRF and SAE form.

Any congenital anomaly/birth defect in a child born to a female subject should be recorded and reported as an SAE.

7.6.1 Woman of Childbearing Potential (WOCBP)

WOCBP includes any female who has experienced menarche and who has not undergone successful surgical sterilization (*e.g.*, hysterectomy, bilateral tubal ligation, or bilateral oophorectomy) or is not postmenopausal. Postmenopausal is defined as ≥12 months with no menses without an alternative medical cause. WOCBP must have a negative UPT at Visit 1 to be enrolled in the study and at Visit 2 to be randomized to study medication.

7.6.2 Protocol approved methods of birth control

The investigator will discuss the potential risk factors associated with pregnancy and the importance of maintaining a highly effective method of birth control with all WOCBP. All WOCBP must use a protocol approved method of birth control throughout the duration of the study and for 30 days after the last study medication application.

For this study protocol approved methods of birth control include:

- Women who are abstinent from reproductive sex as a matter of lifestyle (*i.e.*, women having sex with women); or who are abstinent are acceptable methods of contraception (as these methods, if followed consistently, are at least as effective as hormonal birth control pills)
- Combined (estrogen and progestogen containing) hormonal contraception associated with inhibition of ovulation:
 - o Oral
 - Transdermal
 - Intravaginal
- Progestogen-only hormonal contraception associated with inhibition of ovulation:
 - o Oral
 - o Implantable
 - o Injectable
- Intrauterine device (IUD)
- Intrauterine hormone-releasing system

WOCBP must be on at least 1 protocol approved method of birth control for the following time periods prior to Visit 1:

- Abstinence (≥30 days)
- Implants (on a stable dose for ≥ 30 days)
- Injectables (on a stable dose for \geq 30 days)
- Patches (on a stable dose for ≥ 30 days)
- Combined oral contraceptives (on a stable dose for \geq 30 days)
- Intrauterine devices (inserted for ≥ 30 days).

Prior to trial enrollment the investigator must discuss with all WOCBP the potential risk factors associated with a pregnancy during the study and the importance of avoiding pregnancy during study participation. The subject must sign an informed consent form documenting this discussion. During the trial, all WOCBP will be instructed to contact the investigator immediately if they suspect they might be pregnant (*e.g.*, missed or late menstrual period). If a subject or investigator suspects that the subject may be pregnant prior to study medication administration, the study medication must be withheld until the results of a pregnancy test are available. If pregnancy is confirmed, the subject must not receive study medication and must be discharged from the study.

If, following the first study medication application it is determined that the subject may have been or was pregnant at the time of study medication exposure (including 30 days after the last

study medication application) the investigator must immediately notify the NFlection Medical Monitor and record the pregnancy on a pregnancy surveillance form. While not an AE or SAE, the investigator must report every pregnancy using a pregnancy surveillance form and follow the same reporting procedures as described for reporting an SAE.

Protocol-required procedures for trial discontinuation and follow-up must be performed on the subject unless contraindicated by pregnancy (*e.g.*, x-ray studies). Other appropriate pregnancy follow-up procedures should be considered if indicated. In addition, the investigator must report follow-up information regarding the course of the pregnancy, including perinatal and neonatal outcome on the pregnancy surveillance form. Infants should be followed for a minimum of six weeks.

8 STATISTICAL METHODOLOGY

8.1 Sample Size Determination

This is a Phase 2a safety study designed to evaluate the safety, proof of mechanism, preliminary efficacy and systemic exposure of NFX-179. A maximum of approximately 48 subjects with confirmed EN are planned to be randomized in the study. The sample size is based on practical considerations. The proposed number of subjects takes into account the rarity of the condition and the exploratory nature of the study and is considered adequate to fulfill the objectives of the study.

8.2 Randomization

Subjects will be randomized with a treatment allocation ratio of 1:1:1:1 (NFX-179 Gel 0.05% to NFX-179 Gel 0.15% to NFX-179 Gel 0.50% to Vehicle Gel) for cNF.

8.3 Statistical Analyses

8.3.1 General Approach

All randomized and treated subjects will be assessed in terms of safety and exploratory efficacy.

Descriptive statistics will be produced on relevant screening and baseline data and on demographic characteristics. Safety and exploratory efficacy endpoints will be summarized descriptively by treatment (when applicable) and for all subjects combined and may be analyzed using appropriate parametric or nonparametric inference tests. The primary outcome measure by suppression of p-ERK levels in defined cNF in treatment groups as compared to vehicle group after 4 weeks of treatment will be assessed. A comparison between NFX-179 treated tumors and vehicle treated tumors will also be performed. Summaries and analyses will be based primarily on non-missing data. Extent of exposure using serum levels of NFX-179 will be evaluated.

Details of the proposed statistical analysis will be documented in the Statistical Analysis Plan (SAP), which will be written following finalization of the protocol and prior to any unblinding of data.

As this is an early phase clinical study, additional exploratory analyses not necessarily identified in the SAP may also be performed to support the clinical development program. Any post-hoc, or unplanned, analyses not identified in the SAP will be clearly identified in the Clinical Study Report in accordance with ICH E3.

8.3.2 Baseline Assessment

Descriptive statistics will be performed on relevant Visit 1 and Visit 2 data (*i.e.*, data collected prior to the treatment administration) and on demographic characteristics. There will be no formal comparison of baseline data, that is, no statistical hypothesis testing.

The number and percentage of subjects enrolled in each study site will be presented by diseases classification (*e.g.*, cNF generalized severe, cNF, generalized intermediate).

8.3.3 Efficacy Analyses

The first primary objective is to determine the pharmacodynamic activity of NFX-179 Gel as defined by suppression of p-ERK levels in the Target cNF Tumors in the NFX-179 Gel treatment groups as compared to Vehicle Gel group after 28 days of QD treatment. This will be assessed

by analyzing p-ERK levels at Visit 5 (Week 4). ANOVA models at the subject level will be used to compare mean p-ERK level between each active treatment group and the vehicle treatment group, with treatment as the independent factor. Within each subject, both the mean and the median p-ERK levels will first be calculated across all 5 tumors. The within-subject mean levels will be analyzed in the primary ANOVA model. The within-subject median levels will also be analyzed in a second ANOVA model to assess whether individual tumor outlier values may have an influence on the analysis. Mixed-model repeated measures ANOVA models will also be used to analyze p-ERK data at the tumor level. In addition, p-ERK levels from the untreated tumor for each subject will be used in exploratory analyses to determine whether the inclusion of this reference level in analysis models may increase sensitivity.

The second primary objective is to determine the safety and tolerability of treatment with NFX-179 Gel (0.05%, 0.15% and 0.50%) or Vehicle Gel applied QD for 28 days of treatment. The frequency of dermal safety and tolerability assessments including pain/burning, pruritus, erythema, edema, scabbing/crusting, and vesiculation/erosion will be summarized by treatment group and visit. All data will be listed. The third primary objective of evaluating adverse events will be based on summaries and listings of adverse events by treatment group, as described below under Safety Analyses.

The first secondary objective is to determine the clinical efficacy of NFX-179 Gel defined as the percent change in neurofibroma volume after 28 days of treatment based on tumor size derived from high frequency ultrasound measurements and 3D photographs. This will be analyzed analogously to the first primary endpoint. Analyses will be conducted both on the tumor level and the subject level, as planned for the first primary endpoint.

The second secondary objective is to measure systemic exposure of NFX-179 gel during the clinical study. Plasma concentrations of NFX-179 will be summarized at Visit 5 (Weeks 4) by treatment group.

The third and fourth secondary objectives are to determine the clinical efficacy of NFX-179 Gel defined as the change from baseline in the Subject's Self-Assessment grade and Physician's

Tumor Assessment grade, separately, after 28 days of treatment. Appropriate mixed-model ANCOVAs will be used to compare, for each treated tumor, change from baseline grade between treatment groups, with treatment as the independent factor, baseline value as the covariate, and subject as the repeated factor. ANCOVA models will also be performed on the subject level after first calculating the within-subject mean values across treated tumors. In addition, for each assessment dichotomized analyses will be conducted on the proportion of tumors achieving a grade of Clear, and also the proportion of tumors achieving a grade of either Clear or Almost Clear, after 28 days of treatment. Treatment groups will be compared to vehicle using appropriate mixed-model logistic regression, as well as a Chi-square analysis of within-subject averaged results across tumors.

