Demographic characteristics will be reported for each subject will be collected at Visit 1 (Screening).

PK:

At select sites blood samples for assessment of NFX-179 levels will be collected at Visit 2 (Baseline), prior to the first study medication application, and at Visit 5 (end of treatment).

Tumor excisions: At Visit 5 (end of treatment) the investigator will excise all 6 Study cNF Tumors to assess for p-ERK levels.

Standardized Photography:

Standardized 3-dimensional color photographs to determine the volume, above the surrounding skin, of the 5 Target cNF Tumors will be taken at Visit 1, Visit 2 (Baseline) and Visit 5 (end of treatment).

Statistical Methods

All subjects who are randomized and dispensed study drug will be included in the intent-to-treat (ITT) analysis set. All subjects who are randomized, receive at least 1 confirmed dose of study drug, and have at least 1 post-baseline safety assessment will be included in the safety population. Last observation carried forward (LOCF) will be used to impute efficacy data that are missing post-baseline through Visit 5 (Week 4). Analyses will also be carried out on observed data. No imputations will be made for missing safety data. No adjustments for multiplicity will be made.

Safety:

Safety Endpoints:

- Adverse events
- Local tolerability including:
 - o erythema
 - o edema
 - o scabbing/crusting
 - vesiculation
 - o erosion
 - o stinging
 - o burning
 - o pruritis
- NFX-179 concentration levels in plasma
- Clinical laboratory assessments

Statistical Analyses:

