4.1 Number of subjects

Approximately 56 subjects will be randomized to 1 of the 4 study medication treatment groups at approximately 6 United States (US) investigational centers with the goal of at least 48 subjects completing the study.

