6.3.3 Study cNF Tumor excision for p-ERK levels

At Visit 5, 4 (±1) hours after the Application Completion Time for the last study medication application, the investigator will excise all 6 Study cNF Tumors (5 Target cNF Tumors and 1 Untreated cNF Tumor) to provide tissue samples to assess for p-ERK levels.

For each of the 6 Study cNF Tumors the investigator will shave excise the entire tumor and cut the tissue into 2 halves vertically ensuring that each half contains epidermis and dermis. Half the tissue sample will be immediately frozen, and half will be preserved in formalin following the instructions below:

- Frozen sample:
 - o Immediately freeze half the tissue in liquid nitrogen using forceps to immerse tissue in liquid nitrogen for ∼10 seconds
 - o Place the frozen tissue in a 2mL screw cap cryovial
 - o Immediately freeze on dry ice
 - Store the sample at -80°C until shipment.

• Formalin preserved sample:

O Within 30 minutes transfer half the tissue to a container prefilled with 10%

neutral-buffered formalin

• Store at room temperature until shipment.

The tissue forceps, cryovials and prefilled containers of formalin will be supplied to each

investigational center.

Each sample will be shipped to a NFlection selected laboratory for evaluation of p-ERK

levels. Detailed instructions for labeling, storing and shipping the tissue samples will be

provided to each investigational center prior to the initiation of subject enrollment.

The investigator will manage the excision wounds following her/his standard of care. All

therapies associated with the care for the excision wounds (e.g., local anesthesia, topical

antibiotics, etc.) must be reported as Concomitant Therapies but their use does not need to be

reported as an AE. If an unexpected event that is not normally associated with the excision

procedure occurs (e.g., infection, an event that is out of the ordinary in severity or duration) it

must be reported as an AE, and any associated therapy must be reported as a Concomitant

Therapy.

At Visit 6, the investigator will see the subject for follow-up on the excision wound care.

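### Does the primary p-ERK ANOVA need its error term and its untreated-tumour model spelled out in the protocol?

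*Combined protocol and SAP*

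**What the plan says.** Section 8.3.3 of the combined protocol and SAP, repeated in the synopsis, states that "ANOVA models at the subject level will be used to compare mean p-ERK level between each active treatment group and the vehicle treatment group", treatment being the only factor. p-ERK is first averaged over a subject's five Target tumours, and "The within-subject mean levels will be analyzed in the primary ANOVA model". A second ANOVA uses within-subject medians, and tumour-level mixed models are also planned.

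The sixth, untreated tumour is removed at the same visit: at Visit 5 "the investigator will excise all 6 Study cNF Tumors (5 Target cNF Tumors and 1 Untreated cNF Tumor"). Its role is limited: "p-ERK levels from the untreated tumor for each subject will be used in exploratory analyses", to see whether a reference level sharpens the comparison. For tumour volume, "This will be analyzed analogously to the first primary endpoint".

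The synopsis adds that "No adjustments for multiplicity will be made". Section 4.1 plans about 56 randomised "with the goal of at least 48 subjects completing the study", that is 48/4 = 12 completers per arm. Section 8.3.1 says that "Details of the proposed statistical analysis will be documented in the Statistical Analysis Plan (SAP"), to be written after the protocol is final and before any unblinding. It leaves the choice between parametric and nonparametric tests open.

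**The concern.** The text can be read two ways. The singular in "The within-subject mean levels will be analyzed in the primary ANOVA model" points to one four-arm model with a pooled residual variance. The plural and pairwise wording in "ANOVA models at the subject level will be used to compare mean p-ERK level between each active treatment group and the vehicle treatment group" could also mean a separate two-group ANOVA for each dose.

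The two agree in expectation when variances are equal. They part if p-ERK is suppressed proportionally, so that arms with a lower mean also have a smaller SD. The pooled model then borrows the small variance of the effective doses and applies it to vehicle against an inactive lowest dose, where the true variance is larger. The test of the weakest dose becomes too liberal. With about 12 subjects per arm and no multiplicity adjustment, each contrast is read on its own, so a spurious low-dose signal could pass as proof of mechanism. Volume, analysed in the same way, would inherit the silence.

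The untreated tumour is the only within-subject tissue reference, yet no model form is named for it. That leaves room to pick a covariate, a difference or a ratio after seeing the data.

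**Working it through.** **The plan's own figure.** There is none to reproduce: section 8.1 rests the sample size on practical considerations and gives no power, SD or alpha.

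**Inputs.** From the documents: four arms, 1:1:1:1, 12 per arm, five treated tumours and one untreated tumour per subject. Assumed: two-sided 5% per contrast; lognormal tumour levels with log SD 0.7; within-subject correlation (ICC) 0.1, 0.3 and 0.5; constant coefficient of variation.

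**Analytic size.** If SD is proportional to the arm mean m (vehicle = low dose = 1), the pooled SE over the true SE for low dose against vehicle is r = sqrt(mean of the four m²), and the large-sample error is 2 × [1 − Φ(1.96 r)].

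- Higher doses at 0.8 and 0.6: r = sqrt((1 + 1 + 0.64 + 0.36)/4) = 0.866; error 9.0%.
- Higher doses at 0.5 and 0.25: r = sqrt((1 + 1 + 0.25 + 0.0625)/4) = 0.760; error 13.6%.
- Only the top dose active, at 0.7: r = sqrt((1 + 1 + 1 + 0.49)/4) = 0.934; error 6.7%.

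**Simulated error for an inactive low dose** (20,000 trials per cell; ranges over the three ICCs):

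| Suppression, mid/high dose | Pooled raw, two-sided | Pooled raw, false suppression only | Two-group raw | Welch raw | Pooled log |
|---|---|---|---|---|---|
| None | 4.6–5.0% | 2.4–2.6% | 4.4–4.9% | 4.0–4.6% | 4.8–5.3% |
| 0%/30% | 6.3–6.4% | 3.1–3.2% | 4.3–4.6% | 3.9–4.3% | 4.8–4.9% |
| 20%/40% | 8.4–8.6% | 4.1–4.5% | 4.6–4.7% | 4.2–4.5% | 4.9–5.2% |
| 50%/75% | 13.1–13.2% | 6.5–6.7% | 4.3–4.6% | 4.0–4.3% | 4.7–5.0% |

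Other seeds gave pooled raw figures of 8.0–8.8% and 13.1–13.6% in the last two rows. With 14 per arm they are 8.6–8.8% and 13.6–14.1%.

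Only a false suppression could be taken for activity, and it is about half of the two-sided figure. With every arm inactive there is no inflation.

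**Cost of contrast-specific variances.** Nominal low-dose power when the low dose truly suppresses by 30%, at ICC 0.1, 0.3 and 0.5:

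| Suppression, low/mid/high | Pooled raw | Welch raw | Pooled log |
|---|---|---|---|
| 30%/30%/30% | 61%, 47%, 36% | 53%, 38%, 28% | 63%, 46%, 35% |
| 30%/50%/75% | 72%, 58%, 48% | 53%, 38%, 28% | 63%, 46%, 36% |

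Welch loses 8 to 9 points in the first row and 19 to 20 in the second. Part of the pooled raw figure comes from its small SE, so not all of that is a real loss.

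**Untreated tumour as covariate.** If tumours are exchangeable within a subject, its correlation with the mean of five is r = ICC / sqrt(ICC + (1 − ICC)/5), so r² = 0.036, 0.205 and 0.417. After a degree-of-freedom penalty of 1 + 1/42, the net variance cut 1 − (1 − r²)(1 + 1/42) is 1%, 19% and 40%.

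The covariate is measured after 28 days of self-applied gel. If treated tumours fall to 0.7 of vehicle and the untreated one falls to u, a log-scale ANCOVA removes a share ICC × ln(u)/ln(0.7) of the effect. That is 3%, 9% and 15% at u = 0.9, and 6%, 19% and 31% at u = 0.8.

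**The case for a change.** The strongest case for a change is that p-ERK suppression is a named primary endpoint for each dose, and that stating an error term costs only words. The risky pattern is also credible. Section 1.1 reports strong suppression ex vivo at 0.5% and above, while the trial's two lower strengths lie below anything tested there. When suppression is 30%/50%/75%, the pooled and two-group readings disagree on the low dose in 18% to 20% of simulated trials. Nor is the log scale a complete cure: with an assay background of half the vehicle median, pooled log error rises to 9.1–9.5% in the 50%/75% case.

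The arithmetic stands, but it shows less than it seems to. In that 18% to 20% the low dose is active, and almost all of the disagreement is the pooled model detecting a true effect. When the low dose is inactive, disagreement is 4.5–4.8% (20%/40%) or 8.6–8.9% (50%/75%). The two-model reading is also strained: section 8.3.3 itself explains the plural by naming a primary ANOVA on means and a second on medians. One four-level treatment factor is the ordinary reading. An assay background is a further assumption, and it is best judged from assay data when the SAP is written.

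**Conclusion.** No change to the plan follows. What is missing is detail of the kind a SAP supplies: scale, error term and handling of values near the assay limit. Section 8.3.1 assigns such detail to a SAP written before unblinding. That SAP is not among the documents, so its silence on the point cannot be shown.

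The possible harm is modest. Under SD proportional to the mean, two-sided error for an inactive low dose is about 6% to 13% in the cases above, or about 3% to 7% for false suppression against 2.5%. It arises only when a higher dose is truly active, so the general proof-of-mechanism conclusion would still be right. No dose-selection rule in the documents hangs on this p-value. With equal variances the problem disappears.

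Raw-scale Welch contrasts are a trade-off: they restore the error rate and give up 8 to 20 points of nominal low-dose power. Under the same lognormal assumption, a pooled ANOVA on the log scale already holds about 5%.

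The untreated-tumour analysis has a stated purpose and an exploratory label. Its gain ranges from negligible to large with an unknown ICC. It could absorb part of the effect if that tumour is exposed. The exchangeability behind the gain is also doubtful, since one Target tumour is facial and the untreated one never is. Leaving it exploratory is sound.

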8.3.4 Safety Analyses

Safety and tolerability will be assessed versus baseline conditions and differences between treated tumors. Descriptive statistics will be produced, where applicable. Safety assessments will be summarized across all subjects. Summaries will be provided by treatment for tumor specific safety assessments.

Extent of exposure using serum levels of NFX-179 will be evaluated.

Adverse events noted during the study will be coded to system organ classes (SOCs) and preferred terms (PTs) using the Medical Dictionary for Regulatory Activities (MedDRA) dictionary. The number and percentage of subjects with pre-treatment and treatment emergent AEs (TEAEs) will be summarized by SOC and PT. TEAEs will also be presented as ontreatment and post-treatment. All AE details will be listed. As the risk profile of NFX-179 in humans is unknown and this is a first in human study, all AEs will be considered in determining the safety profile of NFX-179 unless obviously unrelated.

Descriptive summaries of laboratory assessments will be presented for each time point, for actual values and changes from baseline.

Other safety assessments, such as physical examination will also be summarized.

Prior and concomitant medications will be coded using the World Health Organization

(WHO) drug dictionary. Prior and concomitant medications will be listed and summarized by

preferred drug name.

